4.1 Study Design

Prospective, single-center, randomized controlled trial with parallel group design. Randomization is performed in a 2:1 ratio (intervention : control) using a computer-generated randomization list with permuted blocks of variable size (4–6). An additional non-randomized translation arm is conducted for non-German-speaking patients.

Blinding is not possible, as the intervention group receives an additional, visibly different synopsis. However, questionnaire evaluation is performed blinded to group assignment.

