oncOPAL — Oncology Optimized Patient-Accessible Language

Study Protocol

Prospective Randomized Controlled Trial to Evaluate Locally Implemented Large Language Models (LLMs) for Simplifying Patient Communication in Hematology and Oncology

Date: 18.03.2026

Version: 1.0

Study Code: oncOPAL

Principal Investigators

Dr. med. [name]

PD Dr. med. [name]

TUM University Hospital (Klinikum rechts der Isar)

[name]

1 Protocol Synopsis

Short Title	oncOPAL
Title	Prospective Randomized Controlled Trial to Evaluate Locally Implemented Large Language Models (LLMs) for Simplifying Patient Communication in Hematology and Oncology
Study Center	TUM University Hospital (Klinikum rechts der Isar)
Study Design	Prospective, randomized controlled trial with parallel group design. Block randomization 2:1 (intervention : control) with permuted blocks of variable size (4–6). Additionally, a non-randomized translation arm for non-German-speaking patients.
Study Population	Inpatients of the Department of Medicine III (Hematology/Oncology) at TUM University Hospital who receive a discharge letter including the sections Current Status, Medical History, Epicrisis, and Further Management as part of routine clinical care.
Rationale	Up to 40–80% of medical information is not correctly recalled or understood by patients. LLMs can convert medical texts into plain-language versions with high accuracy. However, prospective RCTs evaluating the clinical benefit of LLM-simplified patient synopses are lacking.
Primary Objective	To evaluate the superiority of LLM-generated, simplified patient synopses over standard synopses with respect to patient comprehension.
Intervention	Intervention group: The following sections of the discharge letter are simplified by the LLM system: Current Status, Medical History, Epicrisis, and Further Management. The patient receives the LLM-

	simplified version in addition to the standard synopsis (after physician review). Control group: Standard synopsis only. Translation arm: LLM-simplified and translated synopsis of the same sections.
Sample Size	180 patients (150 randomized: 100 intervention, 50 control; 30 translation arm)
Primary Endpoint	Comprehension score (5-item scale, 10-point Likert, based on PEMAT)
Secondary Endpoints	Patient satisfaction (EORTC QLQ-INFO25 subscales), uncertainty reduction, format preference, physician review workload, correction rate, translation quality

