7.7 Access Control

Access to study data is protected by individual user accounts with strong passwords and is logged. Servers are located in a secured data center with access control.

8 Benefit-Risk Assessment

The benefit-risk ratio is favorable. Participants in the intervention group and translation arm receive an additional plain-language synopsis that can promote understanding of diagnosis and treatment. Study participation involves minimal burden (additional time requirement of approximately 5–15 minutes). There are no physical risks. Psychological risks are low; the risk of possible misunderstandings arising from the simplified presentation is mitigated by mandatory physician review. Routine clinical care remains completely unchanged.

9 Sample Size and Power Analysis

The sample size calculation is based on the following assumptions: a clinically relevant difference in the primary endpoint of 1.5 points, an expected standard deviation of 2.5 points, power of 80%, significance level $\alpha = 0.05$ (two-sided), a randomization ratio of 2:1, and an expected dropout rate of 10%.

For a two-sided t-test for independent samples, the required sample size is $n = 136$ (91 intervention, 45 control). Accounting for the dropout rate, $n = 150$ patients will be recruited for the randomized part.

For the translation arm, $n = 30$ patients will be enrolled. This sample size permits a descriptive evaluation of feasibility without a formal statistical comparison.

10 Funding

The study is funded through internal resources of the Institute for Diagnostic and Interventional Radiology and the Department of Medicine III at TUM University Hospital (Klinikum rechts der Isar). There are no conflicts of interest.

11 References

1. Kessels RPC. Patients' memory for medical information. J R Soc Med. 2003;96(5):219-222.
2. Jeblick K, et al. ChatGPT Makes Medicine Easy to Swallow: An Exploratory Case Study on Simplified Radiology Reports. Radiology. 2024;308(1):e230618.

3. Ayers JW, et al. Comparing Physician and Artificial Intelligence Chatbot Responses to Patient Questions Posted to a Public Social Media Forum. *JAMA Intern Med.* 2023;183(6):589-596.
4. Arraras JL, et al. The EORTC QLQ-INFO25: A questionnaire to assess information given to cancer patients. *Eur J Cancer.* 2010;46(15):2726-2738.
5. Basch E, et al. Overall Survival Results of a Trial Assessing Patient-Reported Outcomes for Symptom Monitoring During Routine Cancer Treatment. *JAMA.* 2017;318(2):197-198.

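### Permuted blocks of 4 to 6 cannot hold a 2:1 ratio: only length 6 works, and one fixed length is not variable

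*Protocol*

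**What the plan says.** Section 4.1 (Study Design) states the ratio and the method together: "Randomization is performed in a 2:1 ratio (intervention : control", and this is done "using a computer-generated randomization list with permuted blocks of variable size (4–6". The study design row of the synopsis says the same: "Block randomization 2:1 (intervention : control) with permuted blocks of variable size (4–6". The sample size row of the synopsis gives the intended result: "180 patients (150 randomized: 100 intervention, 50 control; 30 translation arm".

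Neither place says how a block of 4 or 5 is to be divided between the arms, and neither limits the lengths to multiples of 3. Section 4.1 also describes the setting: "Prospective, single-center, randomized controlled trial with parallel group design", and "Blinding is not possible, as the intervention group receives an additional, visibly different synopsis". Only the evaluation of the questionnaires is blinded. The protocol does not describe who holds the list or how the next allocation is concealed.

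**The concern.** A permuted block carries the allocation ratio because it contains a fixed number of places for each arm. At 2:1 those numbers are whole only when the length is divisible by 3. The stated range of 4 to 6 contains one such length. The two properties the protocol asks for, 2:1 blocks and variable block length, therefore cannot both hold.

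Whoever builds the list has to depart from the text. If 4s or 5s are used with an improvised split, the overall ratio rests on a choice that is documented nowhere. If only 6s are used, the length is fixed and the protection that varying it was meant to give is gone.

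Predictability matters in this trial. Treating staff identify candidates (section 6.3), a study physician obtains consent (section 7.1), and a study physician reviews each simplified synopsis (section 4.3). Past allocations can thus become known close to recruitment, and the block lengths are printed in the protocol. The primary endpoint is comprehension as rated by the patient (section 3.3), which plausibly varies with education and health literacy. Selective approach or timing of enrolment could therefore bias the comparison.

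**Working it through.** **Inputs.** Ratio 2:1 and block lengths 4 to 6 (section 4.1 and synopsis); 150 randomized, planned as 100 and 50 (synopsis); for the power check, a difference of 1.5, a standard deviation of 2.5 and two-sided alpha 0.05 (section 9).

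**Step 1: can each length hold 2:1?** A block of length b needs 2b/3 intervention and b/3 control places.

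| b | Intervention | Control | Possible |
|---|---|---|---|
| 4 | 2.67 | 1.33 | no |
| 5 | 3.33 | 1.67 | no |
| 6 | 4 | 2 | yes |

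For comparison, 3 gives 2:1, 9 gives 6:3 and 12 gives 8:4, all exact.

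**Step 2: overall split if 4s or 5s are used.** Assume equal numbers of each length and scale to 150.

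| Blocks used | Sum | Of 150 |
|---|---|---|
| 4 as 3:1, 6 as 4:2 | 7:3 | 105:45 |
| 4 as 2:2, 6 as 4:2 | 6:4 | 90:60 |
| 4 as 3:1, 5 as 3:2, 6 as 4:2 | 10:5 | 100:50 |
| 4 as 2:2, 5 as 3:2, 6 as 4:2 | 9:6 | 90:60 |
| 4 as 3:1, 5 as 4:1, 6 as 4:2 | 11:4 | 110:40 |

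The planned 100:50 appears for one of these schemes, and even there the blocks of 4 and 5 are not 2:1.

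**Step 3: predictability if only 6s are used.** Once one arm's places in a block are used up, every remaining assignment is certain. The number of certain assignments is the length of the final run of identical assignments. A 4:2 block has 15 orderings:

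- ending in two controls: 1 ordering, run of 2;
- ending in a single control: 4 orderings, run of 1;
- ending in 1, 2, 3 or 4 intervention places: 4, 3, 2 and 1 orderings.

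The run lengths sum to 2 + 4 + (4×1 + 3×2 + 2×3 + 1×4) = 26, so the mean is 26/15 = 1.733. The closed form agrees: 4/3 + 2/5 = 1.733. As a share this is 1.733/6 = 28.9%. With 150/6 = 25 blocks, 25 × 1.733 = 43.3 assignments.

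The same formula for other lengths, if the length is known: a block of 3 gives 2/2 + 1/3 = 1.33 of 3 (44%), and a block of 9 gives 6/4 + 3/7 = 1.93 of 9 (21%).

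**Step 4: does the shift in ratio matter for power?** Normal approximation, 150 patients before dropout: power = Φ(1.5 / (2.5 × √(1/n1 + 1/n2)) − 1.96).

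- 100:50: 1.5/0.433 = 3.46, power about 93%
- 105:45: 1.5/0.445 = 3.37, power about 92%
- 90:60: 1.5/0.417 = 3.60, power about 95%
- 110:40: 1.5/0.462 = 3.25, power about 90%

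With 10% dropout, 110:40 becomes 99:36, and 1.5/0.487 = 3.08 gives about 87%. All exceed the 80% used for planning.

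**The case against.** The protocol gives 2:1 as the ratio of the randomization and does not say that every block must hold it. An equal mix of 4s split 3:1, 5s split 3:2 and 6s split 4:2 reaches exactly 100:50. This is correct, so an overall 2:1 is not ruled out. But the protocol states no such scheme, and its blocks of 4 and 5 are still not 2:1.

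The change in ratio hardly touches the primary test. That stands: power stays well above 80% for every split checked, and a departure from 2:1 does not by itself bias the comparison.

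The 29% holds only if the list uses 6s alone and someone knows this and follows every allocation in order. Recruitment is consecutive (section 6.3), and randomization follows eligibility checks and written consent (section 4.2). This also stands in part: the figure is an upper bound, and selection bias is possible rather than shown. Consent before randomization does not close the gap, because staff still influence whom to approach and when, and concealment is not described.

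Finally, adding blocks of 3 is not an obvious gain, since a block of 3 known to be such reveals 44% of its assignments. That is a fair caution about which multiples to mix. It does not weaken the case for using multiples of 3.

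**Conclusion.** The concern holds. As written, the block lengths contradict the ratio: two of the three permitted lengths cannot be 2:1, and using only the third contradicts variable size. The contradiction appears in both places where the randomization is specified, and nothing elsewhere in the protocol resolves it.

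Its size depends on how the list is built. With improvised splits used in equal numbers, the intervention arm is 90 to 110 of 150 for the schemes checked, with little loss of power. With fixed blocks of 6, up to about 43 of 150 assignments (29%) are certain to someone who knows the length and tracks the sequence. The more serious consequences are that the list cannot be built to the text and that the variable block length may be lost in an unblinded, single-center trial. Allocations already made cannot be corrected later, so this must be settled before the first patient is randomized.

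**What to change.** In section 4.1 and in the study design row of the synopsis, replace the range of 4 to 6 with randomly mixed block lengths that are multiples of 3, using at least two lengths. Lengths of 6 and 9 are a good choice. For example, ten blocks of each in random order give 10 × 6 + 10 × 9 = 150 patients and exactly 10 × 4 + 10 × 6 = 100 intervention and 10 × 2 + 10 × 3 = 50 control. Mixing in 3s also keeps 2:1 but makes those blocks easier to read.

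Preferably the protocol should say only that the blocks vary in length and preserve 2:1, with the actual lengths held in a document that recruiting staff do not see.

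The cost is a one-line correction in two places and a newly generated list. The protocol is dated 18 March 2026 and recruitment is planned from April 2026. If done before the first randomization, nothing else in the design changes, and 100:50 remains attainable because 150 is divisible by 3.

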4.2 Study Procedures

Potential participants are identified during inpatient stays in the Department of Medicine III. Following verification of inclusion and exclusion criteria, informed consent is obtained in writing (with a reflection period of at least 24 hours). Randomization or assignment to the translation arm then follows.

Day 0 (as part of the regular hospital visit):

- Informed consent procedure (approx. 10–15 minutes)
- Randomization or assignment to the translation arm
- Preparation of the synopsis as part of routine clinical care
- LLM simplification and physician review where applicable
- Distribution of synopsis/synopses with at least 15 minutes reading time
- Completion of the questionnaire (approx. 5–10 minutes)

No further study visits are planned. Study participation is complete upon submission of the questionnaire.

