4.4 Technical Implementation

The LLM system (GPT-OSS) is operated locally on servers at the Klinikum rechts der Isar (on-premise). No data are transmitted to external servers or cloud services. The system is not classified as a medical device and is used solely to support text simplification, not for diagnosis or treatment decisions.

5 Criteria for Early Study Termination

Individual Discontinuation:

- Withdrawal of consent by the participant
- Subsequent identification of an exclusion criterion

Termination of the Entire Study:

- Decision by the principal investigators for scientific or organizational reasons
- Request by the responsible ethics committee or supervisory authority
- Unexpected, serious safety concerns

6 Study Population

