6.1 Inclusion Criteria

- Age 18 years or older
- Inpatients of the Department of Medicine III (Hematology/Oncology) at TUM University Hospital
- Receipt of a discharge letter including the sections Current Status, Medical History, Epicrisis, and Further Management as part of routine clinical care
- Capacity to provide informed consent
- Written informed consent following the consent procedure

Additional Inclusion Criteria for the Translation Arm:

- Insufficient German language proficiency
- Native language supported by the LLM system (English, Turkish, Arabic, Russian, Polish, Spanish, Italian, French, Portuguese, Vietnamese, Chinese)

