7.1 Informed Consent

Study participation requires prior written informed consent. The consent procedure is conducted by a study physician. Participants are given a reflection period of at least 24 hours. Consent may be withdrawn at any time without giving reasons and without any disadvantage to further treatment.

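### Section 4.2 randomises before the standard synopsis is prepared, so the arm could influence the comparator text and the letter-based inclusion criterion cannot, read literally, be confirmed before allocation

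*Protocol*

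**What the plan says.** The opening paragraph of Protocol section 4.2 has eligibility verified first, then written consent with at least 24 hours of reflection; "Randomization or assignment to the translation arm then follows". The Day 0 list beneath it runs: consent procedure, randomisation or assignment, "Preparation of the synopsis as part of routine clinical care", LLM simplification with physician review, hand-out with reading time, questionnaire. No further visit is planned.

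Section 4.3 gives the control group the standard synopsis and nothing else. The intervention group gets that same synopsis plus the simplified version, which the LLM makes from four sections of the discharge letter.

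On masking, section 4.1 states: "Blinding is not possible, as the intervention group receives an additional, visibly different synopsis". It then blinds the evaluation of the questionnaires and no other step.

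Section 6.1 lists as an inclusion criterion: "Receipt of a discharge letter including the sections Current Status, Medical History, Epicrisis, and Further Management as part of routine clinical care". Section 7.1 repeats the consent interval: "Participants are given a reflection period of at least 24 hours".

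**The concern.** The treatment contrast is simplified text plus standard text against standard text alone. It isolates the LLM only if the standard text is of the same kind in both arms. Under the listed order, someone writes that text after the allocation exists, and the protocol does not stop that person from knowing it. An author might explain more for a patient who will get nothing else, or take less trouble with wording that the LLM will simplify anyway. The primary endpoint in section 3.3 is the patient's own rating of how well the synopsis is understood, so the plainness of the text acts directly on the outcome. That patients cannot be blinded is unavoidable here; this route is avoidable.

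The same order affects eligibility. A criterion that depends on the content of a letter is hard to confirm before the letter is written, so a patient could be randomised and only afterwards turn out to lack one of the four sections.

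**Working it through.** The point is about sequence. The protocol gives no figure to reproduce, so the check sets the sections side by side.

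1. **When the comparator text is written.** The Day 0 entries in 4.2 are bullets, not numbers, but the order is plainly chronological: simplification comes after preparation, and the questionnaire comes after reading. The opening paragraph independently places randomisation directly after consent. Preparation of the synopsis therefore follows allocation.

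2. **What depends on that text.** From 4.3, it is the whole control condition and one of two documents in the intervention arm. The LLM input is described as four discharge-letter sections. I take the standard synopsis to be those sections or to be drawn from them, because 4.2 moves directly from preparing the synopsis to simplifying it; the protocol does not say so outright.

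3. **Who may know the arm.** Section 4.1 masks questionnaire evaluation only. Section 6.3 has treating staff identify participants, so the people around the letter are close to the trial. No section conceals the arm from the author or locks the text before allocation. Section 8 says routine care is unchanged, which is an assertion and not a procedure.

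4. **Direction.** Let the difference be D = intervention score − control score.
   - Plainer letters for controls raise the control score, so D falls.
   - Less careful letters in the intervention arm lower that arm's score or leave it unchanged, so D falls or stays the same.
   - An author who takes more care because the text will go through the LLM and a physician review would push D up.

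   The first two routes are the more obvious and both dilute. The third cannot be ruled out, so the net direction is uncertain.

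5. **Eligibility.** Section 4.2 puts verification of criteria before consent. Section 6.1 requires a letter containing four named sections. If the letter text is what is prepared in the third Day 0 step, its sections can be seen only two steps after the point at which the protocol says they were checked.

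6. **Consent timing.** The participant steps with a stated time on Day 0 are consent 10–15 min, reading at least 15 min and questionnaire 5–10 min. At the minimum reading time this is 10 + 15 + 5 = 30 min to 15 + 15 + 10 = 40 min. The list shows no interval of 24 h between the consent procedure and randomisation.

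**The case against.** The strongest reply is that the bias is only a possibility. The letter is a routine document, section 4.1 does not say that its authors learn the arm, and the obvious routes work against the intervention. This largely stands: the protocol shows an open route, not a bias that occurs. It does not remove the point, because dilution also damages a superiority trial and closing the route costs almost nothing.

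It can also be said that the letter criterion is meant prospectively, for patients due to receive such a letter as part of usual care. That reading is possible and would fit verification before consent. The protocol does not state it, and the presence of all four sections is still known only once the text exists.

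A reader might infer several stronger things that the protocol does not support:

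- **That section 5 conflicts with the ITT analysis named in the synopsis.** Section 5 provides for individual discontinuation on "Subsequent identification of an exclusion criterion". The letter requirement is an inclusion criterion, nothing in 6.2 concerns the letter, and discontinuation is not removal from the analysis set. Detailed rules on analysis sets commonly sit in the SAP, which is not at hand.
- **That the reflection rule will be breached for every patient.** If information is given a day earlier and only the signature falls on Day 0, the rule is met. The text is ambiguous; a certain breach is not shown.
- **That the order could manufacture a false finding of superiority.** The obvious routes run the other way.
- **That patients lost between allocation and a finished letter would use up the dropout allowance.** The protocol gives no rate at which sections are missing.

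**Conclusion.** The point holds in a limited form. As section 4.2 is written, the standard text is produced after randomisation and its author is not kept unaware of the arm, so the comparator is open to an avoidable influence. Its net direction is uncertain, with dilution the more obvious result. Its size cannot be computed: the protocol has no figure on how letter clarity varies or how far it moves the score. Setting an assumed shift against the 1.5-point target would only restate the assumption. Nor need a change in source clarity carry through one for one in the intervention arm, where patients also read the rewritten version.

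The letter-based criterion has a timing mismatch on its literal reading. The Day 0 consent entry is a secondary matter of wording.

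The conclusion assumes that the Day 0 list is chronological and, for the eligibility part and the link to the LLM input, that the standard synopsis comes from the four letter sections. If the letter were a separate document already complete at consent, the eligibility part would fall away; the control text would still be prepared after allocation.

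**What to change.** Reorder the Day 0 list in section 4.2:

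1. Finalise and lock the four sections and the standard synopsis.
2. Confirm the letter criterion of 6.1 against the locked text.
3. Randomise.
4. In the intervention arm only, run the LLM simplification and physician review.
5. Hand out the text or texts, allow the reading time and collect the questionnaire.

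If randomisation has to stay early for practical reasons, state instead that the author of the standard text is kept unaware of the arm until it is locked. That is weaker, because it does not settle the letter criterion.

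Separately, reconcile the Day 0 consent entry with the reflection period in 4.2 and 7.1, by stating when information is given and when consent is signed relative to randomisation.

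The cost is protocol wording and a later randomisation step, with no added patients, visits or measurements. The small downside is that the randomisation list must be accessible at discharge time. The change belongs before recruitment, since the order of allocation and writing cannot be repaired in the analysis.
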